## 9.13. Other aspects

Not applicable.

## 10. PROTECTION OF HUMAN SUBJECTS

### 10.1. Regulatory and ethical considerations, including the informed consent process

The study will be conducted in accordance with the ICH Guideline for GCP, Guidelines for Good Pharmacoprevention Practices (GPP) [ISPE, 2015], other applicable guidelines, all applicable subject privacy requirements and the guiding principles of the Declaration of Helsinki.

The study has been designed and will be conducted in accordance with the ICH Harmonised Tripartite Guideline for clinical investigation of medicinal products in the paediatric population (ICH E11) and all other applicable country specific regulatory and local ethical committee requirements.

GSK will obtain favourable opinion/approval to conduct the study prior to a site initiating the study in any country, according to local requirements, or will document that neither a favourable opinion nor an approval to conduct the study is needed.

Conduct of the study includes, but is not limited to, the following:

- Independent Ethics Committee (IEC) review and favourable opinion/approval of study protocol and any subsequent amendments.
- Subjects/Subjects' parent(s)/LAR(s) informed consent.
- Investigator reporting requirements as stated in the protocol.

GSK Biologicals will provide full details of the above procedures to the investigator verbally as well as in writing.

Freely given and written or witnessed/ thumb printed informed consent must be obtained from each subject/subjects' parent(s)/LAR(s) or the impartial witness, as appropriate, prior to participation in the study.

GSK Biologicals will prepare a model ICF which will embody the applicable ICH GCP or other applicable guidelines, and GSK Biologicals required elements. While it is strongly recommended that this model ICF be followed as closely as possible, the informed consent requirements given in this document are not intended to pre-empt any local regulations which require additional information to be disclosed for informed consent to be legally effective. Clinical judgement, local regulations and requirements should guide the final structure and content of the local version of the ICF.

The investigator has the final responsibility for the final presentation of the ICF, respecting the mandatory requirements of local regulations. The ICF generated by the

investigator with the assistance of the sponsor's representative must be acceptable to GSK Biologicals and be approved (along with the protocol, and any other necessary documentation) by the IRB/IEC.

## 11. MANAGEMENT AND REPORTING OF ADVERSE EVENTS/ADVERSE REACTIONS

The definitions of the safety endpoints are provided in section 9.3.1.

### 11.1. Detecting and recording medically attended AEFIs, serious AEFIs, pIMDs and pregnancies

#### 11.1.1. Prompt reporting of medically attended AEFIs, serious AEFIs, pIMDs and pregnancy to GSK Biologicals

Any causally related medically attended AEFIs occurring within 30 days following each immunisation with *Cervarix*, serious AEFIs, pIMDs and pregnancies will be reported promptly to GSK as described in [Table 6](#) once the investigator determines that the event meets the protocol definition.

**Table 6 Time frames for submitting medically attended AEFIs, serious AEFIs, pIMDs and pregnancy reports to GSK Biologicals**

Type of Event	Initial Reports		Follow-up Information on a Previous Report	
	Time Frame	Documents	Time Frame	Documents
Causally related medically attended AEFIs	5 days*	Expedited AEFI screen	5 days*	Expedited AEFI screen
All serious AEFIs	24 hours*	Expedited AEFI screen	24 hours*	Expedited AEFI screen
pIMDs	24 hours*	Expedited AEFI screen	24 hours*	Expedited AEFI screen
Pregnancies	24 hours*	Pregnancy report form	24 hours*	Pregnancy report form

\* Time frame allowed after receipt or awareness of the information.

In case the electronic reporting system is temporarily unavailable, a back-up system is in place. Please refer to Section 11.1.4.1 for a detailed description.

Study Contact for Reporting serious AEFIs	
Please see the Sponsor Information Sheet for contact details of who to contact in the event of a serious AEFI. In addition, the GSK Biologicals Clinical Safety Physician can be contacted in an emergency.	
Back-up study contact for reporting serious AEFIs	
GSK Biologicals Clinical Safety & Pharmacovigilance	
Fax: PPD	/ PPD
China Pharmacovigilance	
Fax: PPD	
Email: PPD	
Back-up e-mail ID	
PPD	
24/24 hour and 7/7 day availability	

## 11.1.2. Evaluation of AEFIs

### 11.1.2.1. Assessment of intensity

The investigator will assess the maximum intensity that occurred over the duration of the event for all medically attended AEFIs, serious AEFIs and pIMDs reported during the study. The assessment will be based on the investigator's clinical judgement.

The intensity should be assigned to one of the following categories:

- 1 (mild) = An AEFI/pIMD which is easily tolerated by the study participant, causing minimal discomfort and not interfering with everyday activities.
- 2 (moderate) = An AEFI/pIMD which is sufficiently discomforting to interfere with normal everyday activities.
- 3 (severe) = An AEFI/pIMD which prevents normal, everyday activities (in a young child, such an AEFI would, for example, prevent attendance at school/kindergarten/a day-care centre and would cause the parent(s)/LAR(s) to seek medical advice).

### 11.1.2.2. Assessment of causality

In case of any medically attended AEFI occurring within the 30 days following each immunisation with *Cervarix*, serious AEFI, pIMDs or PO (elective abortion for medical reasons or spontaneous abortion or congenital anomaly), the investigator should assess the causality. The investigator will use clinical judgement to determine the relationship. Alternative causes, such as natural history of the underlying diseases, other concomitant therapy and other risk factors will be considered and investigated. The investigator will

also consult the Product Information (Summary of Product Characteristics) to determine his/her assessment.

There may be situations when a serious AEFI has occurred and the investigator has minimal information to include in the initial report to GSK Biologicals. However, it is very important that the investigator always makes an assessment of causality for every event prior to submission of the serious AEFI to GSK Biologicals. The investigator may change his/ her opinion of causality in light of follow-up information and update the serious AEFI information accordingly. The causality assessment is one of the criteria used when determining regulatory reporting requirements.

Causality should be assessed by the investigator using the following question:

Is there a reasonable possibility that the AEFI/serious AEFI/pIMD may have been caused by the vaccine?

YES : There is a reasonable possibility that the vaccine contributed to the AEFI/pIMD.

NO : There is no reasonable possibility that the vaccine contributed to the AEFI/pIMD. There are other, more likely causes and administration of the vaccine is not suspected to have contributed to the AEFI/pIMD.

Possible contributing factors include:

- Medical history
- Other medication
- Protocol required procedure
- Other procedure not required by the protocol
- Erroneous administration
- Other cause (specify).

### **11.1.3. Regulatory reporting requirements for AEFIs, pIMDs and POs**

The investigator will promptly report all AEFIs (medically attended and serious), pIMDs and POs to GSK in accordance with the procedures detailed in Section 11.1.1. GSK Biologicals has a legal responsibility to promptly notify, as appropriate, both the local regulatory authority and other regulatory agencies about the safety of a product. Prompt notification of serious AEFIs by the investigator to the Study Contact for Reporting serious AEFIs is essential so that legal obligations and ethical responsibilities towards the safety of other subjects are met.

**11.1.4. Completion and transmission of AEFIs, pIMDs and POs report to GSK Biologicals**

Once an investigator becomes aware that an AEFI/pIMD/PO has occurred in a study subject, the investigator will complete and submit the information in the expedited AEFI screen/pregnancy report form within 24 hours. The serious AEFI screens in the eCRF will always be completed as thoroughly as possible with all available details of the event and will be submitted by the investigator. If the investigator does not have all information regarding a serious AEFI, he/she will not wait to receive additional information before notifying GSK of the event and completing the expedited AEFI screens in the eCRF. The expedited AEFI screens should be updated when additional relevant information is received **WITHIN 24 HOURS**.

The investigator will always provide an assessment of causality at the time of the initial report.

**11.1.4.1. Back-up system in case the electronic AEFI, pIMD and PO reporting system does not work**

If the AEFI, pIMD and/or PO reporting system has been down for 24 hours, the investigator or delegate should fax an AEFI/pIMD report form or pregnancy report form directly to the GSK Central Safety department (please refer to Section 11.1.1) within 24 hours. The maximum timeline for reporting AEFIs/pIMDs/POs to central safety is therefore 48 hours.

*Note: This back-up system should only be used if the electronic reporting system is not working and NOT if the system is slow.*

As soon as the electronic reporting system is working again, the investigator or delegate must update the expedited AEFI screens and/or pregnancy report forms in the eCRF within 24 hours.

The final valid information for regulatory reporting will be the information reported through the electronic system.

When additional information is received on an AEFI/pIMD/PO after freezing of the subject's eCRF, new or updated information is to be recorded on the paper AEFI/pIMD/pregnancy Report Form, with all changes signed and dated by the investigator. The updated AEFI/pIMD/pregnancy Report Form should be resent to GSK Biologicals by facsimile **WITHIN 24 HOURS** of receipt of the follow-up information.

In rare circumstances, if the electronic system for reporting AEFIs/pIMDs/POs does not work and in the absence of facsimile equipment, notification by telephone is acceptable, with a copy of the AEFI/pIMD/pregnancy Report Form sent by email or by mail. Initial notification via the telephone does not replace the need for the investigator to complete and submit expedited AEFI screens/pregnancy report forms in the eCRF (or complete and sign the AEFI/pIMD/pregnancy Report Form if back-up system needs to be used).

In the event of a death, determined by the investigator to be related to vaccination, completion of expedited AEFI screens in the eCRF/sending of the fax (if electronic serious AEFI reporting system does not work or after freezing of the subject's eCRF) must be accompanied by telephone call to the study contact for reporting serious AEFIs.

#### **11.1.5. Follow-up of AEFI and serious AEFI**

After the initial AEFI/serious AEFI report, the investigator is required to proactively follow each subject and provide further information to GSK Biologicals on the subject's condition.

All serious AEFIs documented at a previous visit/contact and designated as not recovered/not resolved or recovering/resolving will be reviewed at subsequent visits/contacts until the end of the study.

All AEFIs documented at a previous visit/contact and designated as not recovered/not resolved or recovering/resolving will be reviewed at subsequent visits/contacts until 30 days after the last vaccination.

Investigators will follow-up subjects:

- With serious AEFIs and other AEFIs until the event has resolved, subsided, stabilised, disappeared, or until the event is otherwise explained, or the subject is lost to follow-up/has terminated follow-up.

Clinically significant laboratory abnormalities will be followed up until they have returned to normal, or a satisfactory explanation has been provided. Additional information (including but not limited to laboratory results) relative to the subsequent course of such abnormalities noted for any subject must be made available to the Site Monitor.

GSK Biologicals may request that, the investigator perform or arrange for the conduct of additional clinical examinations/tests and/or evaluations to elucidate as fully as possible the nature and/or causality of the AEFI or serious AEFI. The investigator is obliged to assist.

#### **11.2. Treatment of AEFI**

Treatment of any AEFI is at the sole discretion of the investigator and according to current good medical practice. Any medication administered for the treatment of an AEFI should be recorded in the subject's eCRF.

##### **11.2.1. Time period for detecting and recording medically attended AEFIs, serious AEFIs, pIMDs and pregnancies**

The reporting period of AEFIs will be as per AEFI guidelines and IDM regulations [AEFI, 2010, IDM, 2013].

An overview of the protocol-required reporting periods for medically attended AEFIs, serious AEFIs, pregnancy, PO, congenital anomalies and pIMDs are given in [Table 7](#).

Table 7 Reporting periods for medically attended AEFIs, serious AEFIs, pIMDs and pregnancy outcomes

Study activity	V1	V2	30 days post V2	Call 1 FU (Telephone interview)	Call 1' FU (Telephone interview)	V3	30 days post V3	Call 2 FU (Telephone interview)	Call 2' FU (Telephone interview)	Call 3 FU (Telephone interview)	End of pregnancy	12 months post-delivery (live births)
	D1	M1	M2	31-45 days post 2 nd immunisation (if done within 2.5 months post 1 st imm.) or 2.5 months post 1 st immunisation if 2 nd immunisation was not done by M 2.5	31-45 days post V2. if done > 2.5 m. after V1. (ie outside Cervarix PI schedule)	M6	M7	31-45 days post 3 rd immunisation	31-45 days post V3 if done > 12 m after V1 (ie outside Cervarix PI schedule)	12 months post V3 (if done by M12) or M 24		
Medically attended AEFIs reported during the 30-day period (day 1-30) following each immunisation with Cervarix												
Serious AEFIs reported during the study period												
pIMDs reported during the study period												
Reporting of pregnancy (from enrolment until 60 days post dose 3)												

## CONFIDENTIAL

207350 (EPI-HPV-070 VS CN PMS)

Protocol Amendment 1 Final

Study activity	V1	V2	30 days post V2	Call 1 FU (Telephone interview)	Call 1' FU (Telephone interview)	V3	30 days post V3	Call 2 FU (Telephone interview)	Call 2' FU (Telephone interview)	Call 3 FU (Telephone interview)	End of pregnancy	12 months post-delivery (live births)
	D1	M1	M2	31-45 days post 2 nd immunisation (if done within 2.5 months post 1 st imm.) or 2.5 months post 1 st immunisation if 2 nd immunisation was not done by M 2.5	31-45 days post V2. if done > 2.5 m. after V1. (ie outside Cervarix PI schedule)	M6	M7	31-45 days post 3 rd immunisation	31-45 days post V3 if done > 12 m after V1 (ie outside Cervarix PI schedule)	12 months post V3 (if done by M12) or M 24		
Reporting of pregnancy outcome												
Reporting of congenital anomalies (from enrolment until 12 months post-delivery)												

V: Vaccine dose; D: Day; M: Month; FU: Follow-up; AEFI: Adverse Event Following Immunisation;

\* Pregnancy outcomes will be reported within 1 month post-delivery. 1 year follow-up post-delivery will occur to look for any congenital anomalies.

Type	Medically attended AEFIs/serious AEFIs/pIMDs/PO
Method for reporting medically attended AEFIs, serious AEFIs, pIMDs, pregnancies, PO and birth defects/congenital anomalies	
 
• Patient interview and observation at immunisation visits (events that have occurred since the previous visits or that occur during or just after the visit).
 
• Structured telephone follow-up (events that have occurred after administration of the complete Cervarix course).
 
• Direct reporting by the subject/subjects parent(s)/LAR(s).
 
• Reporting by physician not part of this study: A physician can report a suspected AEFI by contacting the study investigator or his/her delegate).
 

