- Vaccination schedule: Chinese female subjects aged between 9 and **45** years, who consented to participate in the study, are expected to receive three doses of *Cervarix* at 0, 1 and 6 months. The second dose can be administered between 1 month and 2.5 months after the first dose and the third dose between 5 and 12 months after the first dose. The vaccine will be administered intra-muscularly, in the deltoid region of the upper arm.

*Note: Cervarix will be available for purchase at immunisation centres or Point of Vaccination (POV).*

- Data collection: electronic Case Report form (eCRF) will be used to collect data.
- Study duration: The follow-up will be performed from enrolment until either 12 months following the third immunisation or 24 months following the first immunisation with *Cervarix* (whichever occurs first). This represents an individual subjects' total follow-up time between 18 and 24 months for subjects completing the immunisation course (3 doses) as per *Cervarix* PI schedule. Subjects who report exposure to *Cervarix* during pregnancy or pregnancy onset up to 60 days following the last immunisation will be followed-up till end of pregnancy, to observe the PO and for any possible congenital anomalies diagnosed during the first 12 months of the child's life. Thus, in such cases, an extended follow-up beyond 24 months may occur.
- Epoch 001: Prospective data collection (for each subject) starting at Visit 1 (Day 1) and ending either 12 months following the third immunisation or 24 months following the first immunisation with *Cervarix*, whichever occurs first.

The study cohorts and epoch foreseen in the study are presented in [Table 1](#).

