**9.2.4. Outline of study procedures**

The outline of study procedures is presented in [Table 2](#).

Table 2 List of study procedures

Visit Timing	VISIT 1 Day 1	VISIT 2 Month 1 (range 1-2.5 months. post 1 st imm. as per Cervarix PI)	CALL 1 31-45 days post 2 nd imm. (if done within 2.5 months post 1 st imm.) or 2.5 months. post 1 st imm. if 2 nd imm. not done by M2.5	CALL 1' 31-45 days post 2 nd imm. if done > 2.5 months. post 1 st imm. (ie outside Cervarix PI schedule)	VISIT 3 Month 6 (range 5-12 m. post 1 st imm. as per Cervarix PI)	CALL 2 31-45 days post 3 rd imm. (if done by M12) or M13 if 3 rd imm. not done by M12	CALL 2' 31-45 days post 3 rd imm if done > 12 months post 1 st imm. (ie outside Cervarix PI schedule)	CALL 3 12 months post 3 rd imm. (if done by M12) or M24 otherwise
	Imm 1	Imm 2	Telephone FU	Telephone FU	Imm 3	Telephone FU	Telephone FU	Telephone FU
Informed consent obtained from the subject/ subjects parent(s)/LAR(s)	•							
Informed assent from the subject	•							
Check inclusion criteria and exclusion criteria	•							
Medical history and vaccination history a	•							
History-directed physical examination	•							
Collect demography data	•							
Investigator to check for contraindication to subsequent vaccination #	•	•			•			
Vaccination with Cervarix A	•	•			•			
Recording of medically attended AEFIs occurring within 30 days post-vaccination, by investigator		•	•	•		•	•	
Record any concomitant medication/vaccination	•	•	•	•	•	•	•	•
Reporting of serious AEFIs and any pIMDs	•	•	•	•	•	•	•	•
Reporting of pregnancies (outcomes and congenital anomalies) **	•	•	•	•	•	•	•	•
Study Conclusion **								•

• is used to indicate a study procedure that requires documentation in the individual eCRF.

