### 9.3.2. Endpoints

#### 9.3.2.1. Primary endpoint

- Occurrence, intensity and causal relationship to vaccination, of medically attended AEFIs reported during the 30-day period (Day 1-30) following each immunisation with *Cervarix*.

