### 9.4. Data sources

This prospective study will collect data using active and enhanced passive surveillance methods. Following methods will be used to collect data:

- Patient interview and observation at immunisation visits (events that have occurred since the previous visits or that occur during or just after the visit).
  - During the immunisation visit, the investigator will enquire about the occurrence of AEFI or pregnancies (as defined in section 9.3.2) that may have occurred

since the last contact with the subject. The investigator will also report any relevant AEFI that may occur during the visit.

- Structured telephone follow-up: The investigator or other delegated study team member will contact the subject by phone at specific time points to enquire about AEFI and pregnancies (as defined in section 9.3.2). Three rounds of telephone follow-up calls will be scheduled. Additional calls will be organised if any immunisations occur outside the schedule defined in the *Cervarix* PI for China, as detailed below:
  - Call 1 will occur between 31-45 days following the second immunisation or about 2.5 months following the first immunisation with *Cervarix* (if the second immunisation was not performed within 2.5 months).

*Note: In case the second immunisation occurs more than 2.5 months following the first immunisation, Call 1' will be scheduled 31-45 days post second immunisation.*
  - Call 2 will occur between 31-45 days following the third immunisation with *Cervarix*.

*Note: In case the third immunisation occurs more than 12 months following the first immunisation, Call 2' will be scheduled 31-45 days post third immunisation.*
  - Call 3 will occur either 12 months following the third immunisation or 24 months following the first immunisation (whichever occurs first).
- For each planned contact, there should be at least three documented attempts to reach the subject. If any clinically relevant event is reported at the time of the contact, and the event has not been recorded so far, then a follow-up will be made to collect the relevant medical data.
- Direct reporting by the subject/subjects parent(s)/LAR(s).
  - A phone contact number/e-mail id will be provided to the subjects to report AEFI and pregnancy which were not recorded previously by the investigator.
- Reporting by physician not part of this study: A physician can report a suspected AEFI by contacting the study investigator or his/her delegate.

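### The method box in protocol section 11.2.1 confines telephone follow-up to events after the full vaccine course, which contradicts the call schedule used to collect the primary endpoint

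*Protocol*

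**What the plan says.** The primary endpoint (protocol section 9.3.2.1) is "medically attended AEFIs reported during the 30-day period (Day 1-30) following each immunisation with" *Cervarix*, so all three dose windows count.

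Section 9.4 says that the study team "will contact the subject by phone at specific time points to enquire about AEFI and pregnancies", with no limit to women who have finished the course. It then sets the timing: "Call 1 will occur between 31-45 days following the second immunisation or about 2.5 months following the first immunisation with" *Cervarix*, the second option applying when dose 2 has not been given. A late second dose has its own call: "In case the second immunisation occurs more than 2.5 months following the first immunisation, Call 1' will be scheduled 31-45 days post second immunisation".

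In Table 2 (section 9.2.4), the row "Recording of medically attended AEFIs occurring within 30 days post-vaccination, by investigator" is marked at Visit 2, Call 1, Call 1', Call 2 and Call 2'. It is not marked at Visit 1, Visit 3 or Call 3. The same table moves Call 2 to Month 13 if dose 3 is "imm. not done by M12", and puts Call 3 at Month 24 for those women.

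The method box after Table 7 in section 11.2.1 describes the same calls differently: "Structured telephone follow-up (events that have occurred after administration of the complete" *Cervarix* course). Section 9.1 uses the immunisation course to mean three doses. SAP section 4.1 keeps every woman with at least one dose in the Exposed Set.

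**The concern.** Section 11 is the part of the protocol that governs safety reporting, so a site or the author of a call script could reasonably work from it. Read literally, its parenthesis leaves Call 1 and Call 1' with nothing to ask about, and leaves no call in scope for a woman who never reaches dose 3.

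That touches the primary endpoint. Every contact that Table 2 marks for medically attended AEFIs after dose 2 is a telephone call, and so is every contact it marks for a woman who stops after dose 1. An event in such a woman would leave the numerator while she stays in the denominator, so any error would push the percentages down. Section 9.1.1 presents the study as active collection that complements passive pharmacovigilance. For women with an incomplete course, the literal wording would remove most of that active element.

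**Working it through.** **1. The passages side by side**

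| Place | Scope or timing of telephone contact | Fits a post-course limit? |
|---|---|---|
| Protocol 11.2.1, method box | Events after the complete course only | The text in question |
| Protocol 11.2.1, Table 7 column headings | Call 1, including 2.5 months after dose 1 if there was no dose 2; Call 1'; Call 3 at Month 24 if dose 3 was not given by Month 12 | No |
| Protocol 9.4 | AEFIs and pregnancies at each call; Call 1 and Call 1' tied to dose 2 or its absence | No |
| Protocol 9.2.4, Table 2 | Medically attended AEFIs marked at Call 1 and Call 1'; Call 2 at Month 13 and Call 3 at Month 24 without dose 3 | No |
| Protocol 9.1 and SAP 3, design footnotes | Same Call 1, Call 1' and Call 3 timing | No |
| Protocol 9.2.5.2.8 | Serious AEFIs and pIMDs taken at any visit or call, from dose 1 | No |

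Timing check from section 9.1: the latest on-schedule dose 2 is at 2.5 months. Adding 45 days (about 1.5 months) puts Call 1 at about 4 months at the latest, and the earliest on-schedule dose 3 is at 5 months. An on-schedule Call 1 therefore always precedes dose 3.

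**2. Who would be affected if the parenthesis were followed**

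- *Three doses.* Dose-1 events are taken at Visit 2 and dose-3 events at Call 2 or 2', both unchanged. Dose-2 events lose Call 1 or 1'. What remains is the Visit 3 interview, which section 9.4 requires but Table 2 does not mark for medically attended AEFIs. On schedule, Visit 3 falls between 5 − 2.5 = 2.5 and 12 − 1 = 11 months after dose 2, against 31-45 days for the call.
- *Two doses.* Dose-1 events are taken at Visit 2. Dose-2 events lose Call 1 or 1' and the Month 13 call, so no scheduled collection remains.
- *One dose.* There is no Visit 2. Calls at about 2.5 and 13 months are both out of scope, so no scheduled collection remains beyond observation at Visit 1.
- *Serious AEFIs and pIMDs.* Completers are still asked at Visits 2 and 3 and at calls after dose 3. Non-completers have no telephone ascertainment after their last visit, only self-report or an outside physician's report.

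**3. Size**

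Inputs are in protocol section 9.5.1: 6.1% over 72 months in the earlier Chinese efficacy trial, a 90-day observation period, N = 3000.

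The plan's own figure reproduces: 6.1% × 3/72 = 0.254%, or 0.2505% using 90 days and 30.4375 days per month. The protocol uses 0.25%, and 0.0025 × 3000 = 7.5 subjects. The Clopper-Pearson interval for 7.5/3000 is 0.104% to 0.503%, matching Table 4 (0.10% to 0.50%).

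With constant incidence and rare events, each 30-day window contributes 7.5/3 = 2.5 subjects. Let *r* be the share of dose-2 events recovered at Visit 3, and assume that passive reporting recovers none. If everyone completes, captured = 2.5 + 2.5*r* + 2.5:

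| *r* | Captured | Percentage | Lost |
|---|---|---|---|
| 1 | 7.5 | 0.25% | 0 |
| 0.5 | 6.25 | 0.21% | 1.25 |
| 0 | 5.0 | 0.17% (exact 95% CI 0.05% to 0.39%) | 2.5 |

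For non-completers, let *f1* stop after dose 1 and *f2* after dose 2. These shares are assumptions.

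- Expected = 2.5 × [1 + (1 − *f1*) + (1 − *f1* − *f2*)]
- Captured = 2.5 × [(1 − *f1*) + (1 + *r*)(1 − *f1* − *f2*)]

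| *f1* = *f2* | Expected | Captured, *r* = 0 to 1 | Share lost |
|---|---|---|---|
| 5% | 7.125 | 4.625 to 6.875 | 35% to 3.5% |
| 10% | 6.75 | 4.25 to 6.25 | 37% to 7% |

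**The case against.** The strongest reply is that this is one parenthesis in a summary box, outweighed by the rest of the plan. The abstract refers the reader to section 9.4 for surveillance methods. Table 2 requires each marked procedure to be documented in the eCRF, and Call 1 and Call 1' are marked. Table 7, in the same section as the parenthesis, has columns for those calls. A site that follows these texts makes and documents the early calls. This stands: the intended design is clear and consistent, and the fault is one of wording.

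The reply also limits what may be inferred, in three ways.

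- A reader might infer that dose-2 events are removed from the study. They are not. The first bullet of the same box and section 9.4 both have the investigator ask at Visit 3 about events since the previous contact, and direct reports from subjects and outside physicians remain. The fall from 7.5 to 5.0 is the worst case for completers, not an expected loss.
- A reader might take Call 1 as the only marked contact for a woman who stops after dose 1. Table 2 also marks Call 2 at Month 13. That call is excluded by the same parenthesis, so the consequence for her is unchanged.
- A reader might add that women stop because of an event, which would worsen the bias. That is possible, but the documents give no evidence on it.

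The objection does not make the parenthesis harmless. The Visit 3 enquiry is unmarked in Table 2, comes months later than the call, and does not exist for women who do not return.

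**Conclusion.** The parenthesis in section 11.2.1 is wrong as written: it contradicts the protocol's own rules for collecting the primary endpoint and must be reconciled with them. The contradiction itself rests on the text alone and needs no assumption.

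The effect is conditional on a site or script following the parenthesis. In completers, the loss would then lie between zero and about 2.5 of 7.5 expected subjects (0.25% falling to 0.17%), given constant incidence and no passive recovery. SAP section 5.4.1 tabulates by dose, so the dose-2 row would bear all of this loss. One-dose women would lose all scheduled collection after Visit 1, and two-dose women all of it for dose 2. The overall size cannot be fixed because the share of non-completers is not stated. The call script is not among the documents, and nothing in them shows that events would in fact be missed. The planned sample size and the Table 4 and Table 5 intervals do not depend on this sentence.

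**What to change.** In the method box of protocol section 11.2.1, replace the parenthesis on structured telephone follow-up with: *events that have occurred since the previous contact, after any dose of Cervarix, whether or not the course is complete*. This matches section 9.4 and Table 2.

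Confirm that the call script has the same scope. The SAP is dated 4 November 2020 and data collection was planned to end in Quarter 1 2021, so the check should cover the script actually used, with the answer stated in the study report.

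The cost is one line of protocol text and one document check. No calls, data fields, analyses or sample-size figures change.
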